(7) Studies by Merovci, DeFronzo et al (54-56) and Ferrannini et al (34,57) have shown that the increase in plasma ketone concentration can be observed within 24 hours following the initiation of SGLT2i therapy. In the EMPA-REG OUTCOME trial (5), separation of the Kaplan Meier curves for cardiovascular mortality and hospitalization for heart failure was observed within the first three months after starting empagliflozin and clearly was evident within 6 months. Thus, the time course of the rapid metabolic switch to ketone production (34,54-57) is consistent with the early reduction in CV mortality and hospitalization for heart failure in the EMPA-REG OUTCOME trial (5). What is not known is the dose-response relationship between the increase in plasma ketone concentration and its effect on cardiac function in individuals with type 2 diabetes mellitus. In a recent publication Gormesen et al (70) demonstrated that infusion of Na-3-hydroxybutyrate to increase the plasma  $\beta$ -OH-B concentration to  $3.5 \pm 0.5$  mmol/L reduced myocardial glucose uptake by ~50% without affecting palmitate uptake/oxidation in healthy, normal-glucose-tolerant subjects. No measures of cardiac function were performed in this study (70). Using magnetic resonance spectroscopy, we will examine the dose response relationship between the increase in plasma ketone concentration and: (i) parameters of LV systolic/diastolic function and (ii) myocardial glucose metabolism in type 2 diabetic patients with Class II-III New York Heart Association since this information is not available in the literature and is pertinent to the positive CV outcome in the EMPA REG OUTCOME trial (5). Some studies have demonstrated that ketone body oxidation is increased in the failing heart and this has raised concern that a further elevation in plasma ketone concentration may not provide added benefit with respect to myocardial energetics (71). Lopaschuk and Verma (72) have suggested that SGLT2 inhibitors might even reduce myocardial ketone body uptake and oxidation. We believe that the latter is unlikely, since neither SGLT2 mRNA nor SLGT2 protein is found in the heart (73). Lopaschuk and Verma (72) conclude "The *in vivo* relationships between ketone oxidation rates and measures of cardiac structure and function in individuals with diabetes treated with and without SGLT2 inhibition are needed. For now, the fuel hypotheses (to explain the reduction in CV mortality and heart failure in the EMPA REG OUTCOME trial) is tantalizing" but still a hypothesis. In the present grant, we will directly examine this hypothesis by providing quantitative information about myocardial function, metabolism, and energetics in type 2 diabetic patients with New York Association Class II-III heart failure following intravenous infusion of  $\beta$ -OH-B to span the physiologic and pharmacologic range of plasma  $\beta$ -OH-B concentrations.

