**Table 1. Events for subjects in GROUPS I and III:**

Visit	Visit 1	Visit 2
Assessments	Screening	MRI Study 1
Schedule	DAY -30 to -7	Day 0-30
Routine Blood Chemistries, CBC, UA, lipid profile, TSH/ T4, A1c, NT-proBNP, hCG	X	
ECG, DXA, ECHO (if not done within 3-6 months of screening)	X	
Vital signs	X	X
Baseline Cardiac MRI and baseline blood samples $\times$ 3: $\beta$ -OH-butyrate, acetoacetate, glucose, FFA, lactate, pyruvate, glycerol, HCO 3 , insulin/C-pep, glucagon, renin and aldosterone		X
Blood safety monitoring before (3 samples) and after (3 samples) the infusion: glucose, potassium with iSTAT		X
Prime-continuous infusion of $\beta$ -OH-B (0.8 M solution; pH adjusted to 7.24) to increase the plasma $\beta$ -OH-B concentration by GROUP I: ~0.5 mmol/L (6-hrs) GROUP III: ~5.0 mmol/L (3-hrs)		X
Post-infusion Cardiac MRI and blood samples $\times$ 3: NT-proBNP, $\beta$ -OH-butyrate, acetoacetate, glucose, FFA, lactate, pyruvate, glycerol, HCO 3 , insulin/C-pep, glucagon, renin and aldosterone		X

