**Table 2. Events for subjects in GROUP II:**

Visit Assessments Schedule	Visit 1 Screening DAY -30 to -7	Visit 2 MRI Study 1 Day 0-30	Visit 3 MRI Study 2 Day 7-30 after MRI Study 1	Visit 4 PET Study 1 Day 7-30 after MRI Study 2	Visit 5 PET Study 2 Day 7-30 after PET Study 1
Routine Blood Chemistrys, CBC, UA, lipid profile, TSH/T4, A1c, NT-proBNP, hCG	X				
ECG, DXA, ECHO (if not done within 3-6 months of screening)	X				
POC urine pregnancy test				X	X
Vital signs	X	X	X	X	X
Baseline Cardiac MRI and baseline blood samples $\times$ 3: $\beta$ -OH-butyrate, acetoacetate, glucose, FFA, lactate, pyruvate, glycerol, HCO 3 , insulin/C-pep, glucagon, renin and aldosterone		X	X		
Blood safety monitoring before (3 samples) and after (3 samples) the infusion: glucose, potassium with iSTAT		X	X	X	X
6-hour prime-continuous infusion of $\beta$ -OH-B (0.8 M solution; pH adjusted to 7.24) to increase the plasma $\beta$ -OH-		X		X	
6-hour prime-continuous infusion of NaHCO 3 (0.12 M solution); volume to be infused will be the same as $\beta$ -			X		X
Post-infusion Cardiac MRI and blood samples $\times$ 3: NT-proBNP, $\beta$ -OH-butyrate, acetoacetate, glucose, FFA, lactate, pyruvate, glycerol, HCO 3 , insulin/C-pep,		X	X		

18F-2-DOG/15O-H 2 O PET study and blood samples x 12: NT-proBNP, $\beta$ -OH-butyrate, acetoacetate, glucose, FFA, lactate, pyruvate, glycerol, HCO 3 and hematocrit (with iSTAT), insulin/C-pep and glucagon, erythropoietin, urine 18F-radioactivity.				X	X
---	--	--	--	---	---

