glucose, FFA, lactate, pyruvate, glycerol, HCO3, insulin, glucagon, renin and aldosterone. Axial and sagittal localizer views, standard two-, three-, and four-chamber views, with 7 mm thick slices are obtained using gradient echo sequence (2.2 x 1.3 mm^2 pixel). Cine imaging with retrospective gaiting is used with a balanced steady-state free precision sequence (TR/TE = 2.44/1.22 ms). Acquisitions consist of 25-30 cardiac phases, matrix 224 x 288, FOV 336 x 430 mm^2, 1.5 x 1.5 mm^2 pixel area. Contiguous short-axis slices are acquired during repetitive breath-holds at expiration. Mitral inflow images are obtained using phase-contrast gradient-echo (PCGE) sequence with through-plane velocity encoding (Venc = 100 cm/s) at the mitral valve with flip angle = 10° and TR/TE = 5.8/3.6 ms. PCGE slice thickness was 8 mm with typical FOV = 228 x 430 mm^2, matrix = 192 x 102, producing 2.89 x 2.89 x 8.0 mm pixel volumes.

Following completion of the baseline MRI, subjects will be divided into three groups (19 subjects per group). Each group will receive a 6-hour (3-hour in group III) prime-continuous infusion of racemic  $\beta$ -OH-B (100 mg/mL solution; pH adjusted to 7.4) to increase the plasma  $\beta$ -OH-B concentration by ~0.5, ~2.0, and ~5.0 mmol/L (43,74).

GROUP I: Prime = 0.4 mg/kg.min for 20 minutes and constant rate = 0.2 mg/kg.min until study end

GROUP II: Prime = 1.5 mg/kg.min for 20 minutes and constant rate = 0.75 mg/kg.min until study end

GROUP III: Prime = 4.0 mg/kg.min for 20 minutes and constant rate = 2.0 mg/kg.min until study end

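### The text supplied gives no random or concealed assignment to the three dose groups and no random order for the Group II MRI infusions, and the text and Table 2 disagree on PET order

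*Combined protocol and SAP*

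**What the plan says.** **Dose group.** The only assignment sentence is in the Study Protocol: "Following completion of the baseline MRI, subjects will be divided into three groups (19 subjects per group". The groups are defined by target rises in plasma β-OH-B of about 0.5, 2.0 and 5.0 mmol/L. Under Rationale, item 7, the investigators state that "we will examine the dose response relationship between the increase in plasma ketone concentration and" cardiac function and myocardial glucose metabolism. The Statistical Analysis section plans an ANOVA of EF change across the three infusion groups, and Expected Results predicts a dose-response.

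**Group II MRI pair.** Group II has two MRI days, one per infusion. Table 2 marks β-OH-B at Visit 2 (MRI Study 1). The NaHCO3 row, "6-hour prime-continuous infusion of NaHCO 3 (0.12 M solution); volume to be infused will be the same as" the β-OH-B volume, is marked at Visit 3: "Visit 3 MRI Study 2 Day 7-30 after MRI Study 1". The Study Protocol describes the NaHCO3 infusion as a time control. It plans none for the low and high doses, but keeps that option open depending on results.

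**Group II PET pair.** The PET section describes a repeat FDG study with NaHCO3 after about 14-30 days and says the two studies are done in random order. Table 2 marks β-OH-B at Visit 4 and NaHCO3 at Visit 5, with the interval "Visit 5 PET Study 2 Day 7-30 after PET Study 1". The PET section also lets the PET studies precede the MRI studies if scanner availability requires it.

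**The concern.** A dose-response conclusion drawn from three separate groups needs groups that would have responded alike to the same dose. Here the group is chosen after a baseline MRI that is meant to confirm EF, so the person choosing may already know the EF. The burden is also unequal: two visits for Groups I and III, five for Group II including two PET studies. Nothing stated stops severity or willingness from sorting patients into groups.

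In Group II, the NaHCO3 session is the only firmly planned within-subject control for elapsed time and infused volume. If it always comes second, a change that depends on session cannot be told apart from a ketone effect. One possible source is getting used to the acquisition, in which "Contiguous short-axis slices are acquired during repetitive breath-holds at expiration".

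For PET, FDG is injected once per session, so glucose uptake can be compared only between sessions. The order therefore has to be unambiguous.

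**Working it through.** **1. Which randomisation statement covers what.** The documents contain one sentence on random order. It stands in the PET section, directly after the repeat FDG study with NaHCO3, so the two studies it refers to are the PET pair. The Group II MRI days come in the next paragraph, with no order given. The permission to do PET before MRI concerns the modality, not which infusion comes first within a pair.

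**2. What cancels in the dose comparison.** The ANOVA is on EF change, so stable differences between groups largely drop out. The baseline-EF route can be sized from the Sample Size inputs (SD 2 points, correlation 0.96). For a baseline imbalance of one SD:

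- regression to the mean = (1 − 0.96) × 2 = 0.08 EF points;
- target effect, read as a relative change = 10% × 45 = 4.5 EF points.

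On those inputs this route is negligible. What remains is effect modification, meaning groups that respond differently for reasons other than dose. No input in the documents gives its size.

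**3. Share of a session effect in the Group II MRI contrast.** Let τ be the ketone effect and π₁, π₂ the mean change from baseline in sessions 1 and 2 that is due to session alone. For each subject, D = change on β-OH-B minus change on NaHCO3.

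- β-OH-B first: E(D) = τ + (π₁ − π₂)
- NaHCO3 first: E(D) = τ − (π₁ − π₂)
- Mean of D with n₁ and n₂ subjects per order: τ + [(n₁ − n₂)/n](π₁ − π₂)

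Each session has its own baseline MRI, so a constant shift between sessions is already removed. Only a difference in change, π₁ ≠ π₂, matters. The documents give 19 per group (Study Protocol) and 23 evaluable or 26 recruited (Sample Size), so all three are shown.

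| Order | Share of (π₁ − π₂) left, no period term |
|---|---|
| All β-OH-B first (Table 2) | 100% |
| 9/10 (n = 19) | 1/19 = 5.3% |
| 11/12 (n = 23) | 1/23 = 4.3% |
| 13/13 (n = 26) | 0 |
| 13/10 (3 of 26 lost from one order) | 3/23 = 13% |

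Averaging the two sequence means, which is what a period term does, makes the share 0 for any split that has both orders.

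**4. Price of the period term.** Ratio of interval widths with and without period = √[n(1/n₁ + 1/n₂)/4] × t(0.975, n − 2)/t(0.975, n − 1).

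- 9/10: 1.0014 × 2.1098/2.1009 = 1.0056
- 11/12: 1.0009 × 2.0796/2.0739 = 1.0037
- 13/13: 1.0000 × 2.0639/2.0595 = 1.0021
- 13/10: 1.0086 × 2.0796/2.0739 = 1.0114

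**5. PET interval.** Table 2 allows days 7 to 30 (24 days); the text says about 14 to 30 (17 days). Days 7 to 13, 7 of the 24, are in conflict. The text's limit is approximate, so the boundary is soft.

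**The case against.** The strongest reply is that the tests carrying the sample size compare each subject with their own baseline in the same session, so neither assignment nor order touches them. That stands in full. MRI reading is also blinded (Data Analysis). That limits reader bias, but it does not make groups comparable or remove a session effect.

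Table 2 may be schematic: the PET text already departs from it on order, and PET may precede MRI. This is fair, and the 100% share holds only if the table is followed. But no note says the infusions may swap, and for MRI no text offers another order.

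It can also be said that the NaHCO3 session is not the sole separation of ketone from elapsed time, because Groups I and II share the 6-hour infusion and the re-scan after 5 hours. That is correct. However, it is a between-group contrast that depends on the assignment in question, and it does not control for volume.

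Finally, a title page was removed before review and might mention randomisation. The point is therefore limited to the text supplied.

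A reader might go further and infer that patients will be selected into dose groups, or that carryover biases the control session. The documents support neither. Silence on method is not evidence of selection. Sessions are at least 7 days apart, and steady state is expected within 60 minutes.

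**Conclusion.** The point stands, limited to two comparisons: the between-dose ANOVA with its dose-response reading, and the Group II β-OH-B versus NaHCO3 contrast. No size of bias can be given for the first beyond the baseline-EF route, which is about 0.08 EF points for a 2-point imbalance if the Sample Size inputs are right. For the second, the size is a share of an unknown and possibly zero session effect: 100% if Table 2 binds, 0 to 5.3% with a balanced random order, and 0 with period modelled. PET is a matter of reconciliation, since the text already randomises it.

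A reader might conclude that the study's efficacy tests are invalid. They are not: the before-and-after comparisons remain as planned. Nor would randomising the groups make the dose-response reading clean. "Each group will receive a 6-hour (3-hour in group III) prime-continuous infusion of racemic" β-OH-B, so Group III is re-scanned after 2 hours and the others after 5. That 3-hour gap goes with dose whatever the assignment. It is a separate limit and should be recorded as such.

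The changes should be made before enrolment, because neither gap can be fully repaired afterwards.

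**What to change.** 1. Assign dose group from a concealed, computer-generated 1:1:1 list once eligibility is confirmed. If this is not done, label the between-dose comparisons non-randomised and limit the dose-response conclusion. Adjusting for baseline EF alone is not an adequate substitute, because on the plan's own inputs it corrects very little and it leaves other imbalances untouched.
2. Randomise the infusion order of the Group II MRI pair in balanced blocks.
3. Reconcile Table 2 with the PET section on order and interval, for example by labelling the paired visits Infusion A and Infusion B.
4. Name the Group II β-OH-B versus NaHCO3 comparison in the Statistical Analysis, with period in the model: change from session baseline for MRI, between-session value for FDG uptake.
5. Note Group III's shorter infusion and earlier re-scan as a limit on the dose-response reading, or handle it as a separate point.

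The cost is two lists and some wording, with no extra patients, visits or scans. The period term takes 1 df and widens the Group II interval by about 0.2 to 0.6%, or 1.1% at a 13/10 split. The real downside is less scheduling flexibility, because the re-scan time depends on the group drawn. Consenting before the group is known is not a new burden: the plan already takes consent at screening and divides subjects later.

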These 3 infusion rates were chosen to cover the range of observed increments in plasma ketone concentrations in type 2 diabetic patients treated with a SGLT2 inhibitor: a  $\beta$ -OH-B increment of ~0.5 mmol/L typically is seen in diabetic individuals treated with an SGLT2 inhibitor, while a  $\beta$ -OH-B increment of 2-5 mmol/L is observed in ~5-10% of individuals (54-62). After 5 (or 2) hours of  $\beta$ -OH-B infusion, the cardiac MRI will be repeated. All baseline blood samples will be repeated at 360, 365, and 370 minutes (6 hours) or at 180, 185, and 190 minutes (3 hours) after the start of the  $\beta$ -OH-B infusion. Based upon prior studies from our group (42), we expect to reach steady state levels of  $\beta$ -OH-B in 60 minutes; this will be documented by measuring  $\beta$ -OH-B (and acetoacetate) levels every 30-60 minutes throughout the study. From the study of Gormesen et al (70), we know that 6 hours is sufficient to see a significant reduction (by 50%) in myocardial glucose uptake in normal-glucose-tolerant subjects. Blood glucose and electrolytes are monitored throughout the study with the instantaneous-result device (iSTAT Handheld Analyzer), and potassium supplement may be given before the start of the  $\beta$ -OH-B infusion to prevent decrease in blood potassium level. The investigator will decide to give 20-40mEq of KCL to subjects with initial potassium in the low limit of normal. The investigator will make this decision based on the risk of the subject to develop low serum potassium based on their medical history and renal function. The contraindication for KCL supplementation is elevated blood potassium. It is unlikely that diabetic patients w not taking an insulin secretagogue (i.e. sulfonylureas) will develop hypoglycemia.

Therefore, individuals with history of taking insulin secretagogues (i.e. sulfonylureas) will have hourly glucose monitoring during the  $\beta$ -OH-B infusion to ensure early detection of hypoglycemia. If at any time a subject develops any symptoms suggestive of hypoglycemia (i.e. anxiety, diaphoresis, hunger, weakness etc.) glucose will be measured immediately. If hypoglycemia occurs, we will treat subjects with 15 grams of rapid acting carbohydrates (i.e. juice), and re-check subject's blood glucose level in 15 minutes, and repeat if necessary, until normoglycemia has been reached.

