## Statistical Analysis

Data are expressed as mean  $\pm$  SD or as percentages. Statistical analyses will be performed using R 3.2.1 statistical software with RStudio IDE, Version 0.99.467. Paired, two-sided Student's t-test will be used to evaluate the null hypothesis of no difference between baseline and post  $\beta$ -OH-B butyrate protocol.  $p<0.05$  is deemed significant. Pearson's product-moment correlation will be used to examine the relationship between changes in parameters of LV diastolic and systolic function and coronary blood versus changes in myocardial  $\beta$ -OH-B uptake and both univariate and multivariate ANOVA for changes in EF in the 3 different  $\beta$ -OH-B infusion groups.

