## Expected Results

Studies in rodent models of heart failure and in humans with heart failure (31,33,38,39,71,83-86) have demonstrated that ketone utilization by the failing heart is increased. However, no study in humans has examined the effect of exogenous infusion of ketones on myocardial function and myocardial glucose utilization in nondiabetic or type 2 diabetic patients with heart failure. We expect that ketone infusion to elevate the plasma ketone concentration by physiologic (+0.5 mmol/L) and pharmacologic (+2.0 and +5.0 mmol/L) levels will cause a dose-response increase in parameters of LV diastolic/systolic function and a dose-response decrease in glucose utilization ( $^{18}\text{F}$ -2-DOG). Although not measured in the present study, we also would expect increased myocardial  $\beta$ -OH-B uptake to complete with fat oxidation since they share a common intermediate, i.e. acetyl CoA, that feeds into the Krebs Cycle. Because of its favorable P/O ratio and other potential metabolic benefits (17,18), we also expect that multiple parameters of LV diastolic (E/A ratio, diastolic volume, peak LV filling rate), as well as systolic (cardiac index, EF, peak LV ejection rate), function will increase. The present results will allow us to define the plasma  $\beta$ -OH-B concentration at which the substrate's beneficial effects on CV function are observed. We anticipate that elevation of the plasma  $\beta$ -OH-B level to 2.0-5.0 mmol/L, i.e. levels that are observed in 5-10% of individuals treated with SGLT2 inhibitors, will elicit a significant improvement in multiple parameters of LV systolic and diastolic function. If so, the "ketone hypothesis" (17,18) would be supported and explain, at least in part, the beneficial effect of empagliflozin and canagliflozin on hospitalization for heart failure and CV mortality in the EMPA REG OUTCOME and CANVAS studies. If beneficial effects on myocardial function are observed with the low dose  $\beta$ -OH-B infusion (increment in plasma  $\beta$ -OH-B =  $\sim$ 0.5 mmol/L), this will allow the results to be generalized to the great majority of diabetic patients treated with SGLT2 inhibitors. A potential limitation of the present study is the relatively small number of diabetic subjects in each of the three groups. However, given the reproducibility of cardiac MRI and its close agreement with the same parameters derived by echocardiography (76), as well as the reproducibility of the measurement of myocardial  $^{18}\text{F}$ -2-DOG uptake (19), we believe that the sample size (see below) will be sufficient to demonstrate significant effects of  $\beta$ -OH-B infusion on myocardial uptake of glucose, as well as on myocardial function. Lastly, we think that it is possible, although unlikely, that even the highest  $\beta$ -OH-B infusion rate (5.0 mmol/kg.min) may not have any effect on cardiac function even though myocardial  $\beta$ -OH-B uptake is increased and glucose uptake is reduced. If so, this would argue against a role for enhanced myocardial ketone uptake in the CV benefit of empagliflozin and canagliflozin in the EMPA-REG OUTCOME and CANVAS studies (5). Alternatively, it is possible that  $\beta$ -OH-B must be infused for longer than 6 hours to observe its beneficial effects on myocardial function. If the high  $\beta$ -OH-B infusion rate fails to increase parameters of LV function, we are prepared to admit diabetic patients to the CRC for a 72 hour  $\beta$ -OH-B infusion prior to performing the cardiac MRI.

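### Contrasts involving Group III confound ketone level with infusion duration, so a flat or lower response at +5.0 mmol/L cannot be attributed to level

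*Combined protocol and SAP*

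**What the plan says.** The durations differ by group in two places. Table 1 gives "GROUP I: ~0.5 mmol/L (6-hrs) GROUP III: ~5.0 mmol/L (3-hrs", and the Study Protocol says "Each group will receive a 6-hour (3-hour in group III) prime-continuous infusion of racemic" β-OH-B. Table 2 gives Group II a 6-hour infusion.

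The measurements follow the infusion. The repeat MRI comes "After 5 (or 2) hours of" β-OH-B infusion. Blood is drawn from 360 minutes ("6 hours) or at 180, 185, and 190 minutes (3 hours) after the start of the" infusion). The natural reading is MRI at 5 h in Groups I and II and at 2 h in Group III. No reason is given for the shorter Group III infusion.

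Group II also has a bicarbonate session as a time control. The Study Protocol plans none for the low- and high-dose groups, but says controls may be added there in the light of results.

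Statistical Analysis lists paired t-tests of baseline against post-infusion values, and then "both univariate and multivariate ANOVA for changes in EF in the 3 different" infusion groups. It has no provision for duration. Expected Results anticipates a dose-response across +0.5, +2.0 and +5.0 mmol/L. It says of a null at the highest rate: "If so, this would argue against a role for enhanced myocardial ketone uptake in the CV benefit" of the SGLT2 inhibitors.

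**The concern.** A dose-response reading needs groups that differ in level and in nothing else that could move ejection fraction (EF). Group III is infused for half as long and imaged 3 hours earlier than the other two. Its EF change can reflect the higher level, the shorter time at that level, or the shorter elapsed time fasting and lying down.

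The case that matters most is a flat or lower Group III response. It could mean that the higher level adds nothing, or that 2 hours was too short. The plan's broad conclusion about the ketone hypothesis rests partly on this group, and its data cannot separate the two explanations.

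**Working it through.** The plan gives no exposure figure to reproduce, so the check starts from its rates and times.

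**1. Can the analysis separate level from duration?** Target increments are 0.5, 2 and 5 mmol/L; MRI times are 5, 5 and 2 h. Duration is fixed by group, so a model with three group effects plus duration has four columns and rank 3: duration cannot be adjusted for. Replacing the group factor by a straight line in level gives three parameters for three group means. That identifies duration only by assuming linearity, and it leaves nothing to test the shape. Across the three groups, level and MRI time correlate at −7.5/√(10.5 × 6) = −0.945.

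**2. Time on plateau.** The Study Protocol expects steady state in 60 minutes. Time on plateau at MRI start is 5 − 1 = 4 h in Groups I and II, and 2 − 1 = 1 h in Group III.

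**3. Mass infused by MRI start.** The rates are of the form "GROUP I: Prime = 0.4 mg/kg.min for 20 minutes and constant rate = 0.2 mg/kg.min until study end". Mass = prime × 20 + constant rate × (minutes to MRI − 20):
- Group I: 0.4 × 20 + 0.2 × 280 = 64 mg/kg
- Group II: 1.5 × 20 + 0.75 × 280 = 240 mg/kg
- Group III: 4.0 × 20 + 2.0 × 100 = 280 mg/kg

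Group III against Group II is 5/2 = 2.5 by target level and 2.0/0.75 = 2.67 by constant rate, but 280/240 = 1.17 by mass received.

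**4. Cumulative exposure.** Take exposure = target × (time − r), where r is the hours of full exposure lost while the level rises, assumed equal in all groups.

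| Assumption | I | II | III (mmol·h/L) |
|---|---|---|---|
| To MRI start, r = 0 | 2.5 | 10 | 10 |
| To MRI start, r = 0.5 (linear rise over 60 min) | 2.25 | 9.0 | 7.5 |
| To end of infusion, r = 0.5 | not needed | 2 × 5.5 = 11.0 | 5 × 2.5 = 12.5 |

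Groups II and III are similar, and their order depends on the ramp and the cut-off.

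**5. Drift unrelated to ketones.** Suppose EF drifts by b points per hour in every group. The drift adds 5b to Groups I and II and 2b to Group III, so it shifts III minus II by −3b and leaves I versus II untouched. The documents give no value of b. For an assumed size of 0.1 to 0.5 points per hour, the shift is 0.3 to 1.5 EF points in size. For scale, the Sample Size section's 10% increase on a baseline of 45% is 4.5 points if relative.

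**The case against.** The strongest reply is that the plan's dose variable is plasma concentration. Steady state is expected in 60 minutes and is checked every 30 to 60 minutes, so both scans start on plateau and the 1:4:10 contrast in level holds at imaging. That stands. It would settle the matter only if the functional effect were immediate, and Expected Results allows that it may need longer than 6 hours.

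Four stronger readings are tempting, and the documents do not support them:
- *Group III has less exposure than Group II.* This follows only with an assumed ramp and a cut-off at MRI start. Without the ramp the two tie, and by the end of infusion the order reverses.
- *The plan reads any null in Group III as a failure of dose.* The statement is conditional on raised ketone uptake and reduced glucose uptake. The next sentence offers duration as an alternative, with a 72-hour infusion as follow-up. What remains is that this alternative is framed around 6 hours while the highest-rate group gets 3. Also, glucose uptake by PET is planned only in Group II, so that part of the condition is not checked in Group III.
- *The plan's own evidence shows that 3 hours is too short.* The sentence "we know that 6 hours is sufficient to see a significant reduction" concerns myocardial glucose uptake in normal-glucose-tolerant subjects, not EF. It neither supports nor rules out 2 to 3 hours for cardiac function.
- *The three groups can show nothing about dose.* Groups I and II are matched on duration and MRI time. If effects only grow with time and nothing else drifts, the short infusion works against Group III, so a clearly larger response there would still suggest a level effect.

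The optional bicarbonate controls could address drift if run at the Group III timing. They depend on results, and they would not equalise time at the ketone level.

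**Conclusion.** The concern holds for contrasts that involve Group III. Level and duration change together there, and no model of the three groups can separate them without an untestable assumption. At MRI start Group III has spent about 1 h on plateau against 4 h, and has received 1.17 times Group II's mass for 2.5 times its target level. These figures rest on the stated rates, the 60-minute steady state, and the reading that the 2-hour scan belongs to Group III.

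A flat or lower Group III response cannot be attributed to level. A clearly larger one may suggest a level effect, provided effects only grow with time and there is no drift unrelated to ketones. The size and direction of any bias in EF are unknown. Group I versus II is free of this problem, but the Study Protocol says only that subjects are divided into groups, with no mention of randomisation, so that contrast carries its own caveat.

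**What to change.** Leave the schedule to the clinical team, and ask them to reconcile the unequal durations with the dose-response claim.

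In Statistical Analysis:
- Name Group I versus Group II as the duration-matched level contrast, and state how subjects are allocated to groups.
- Keep the three-group ANOVA as a secondary analysis.
- Report Group III's within-patient change, and label it and its contrasts with the other groups as differing in both level and duration.

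In Expected Results:
- Correct the duration caveat, since the highest-rate group is infused for 3 h and imaged at 2 h.
- State that a null in Group III does not by itself argue against the hypothesis unless the durations are made comparable.

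This changes analysis and interpretation text only, and needs no extra patients or visits. The price is a smaller claim: a matched two-level contrast plus a qualified Group III estimate, in place of a three-level dose-response.
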